## **9 DRUG INFORMATION - NIVOLUMAB**

### **9.1 DRUG ORDERING AND ACCOUNTABILITY**

BMS is supplying study drug. Please see the pharmacy manual for instructions on how to order study drug from BMS.

### **9.2 PRODUCT DESCRIPTION AND DOSAGE FORM**

Nivolumab (BMS-936558-01) Injection drug product is a sterile, non-pyrogenic, single-use, isotonic aqueous solution formulated at 10 mg/mL.

- **Other names:** MDX-1106, ONO-4538 and antiPD-1.
- **Potency:** 100mg/Vial (10mg/mL)
- **Primary Packaging (volume)/Label type:** Carton of 5 or 10 vials
- **Secondary packaging (Qty)/Label type:** 10-cc Type 1 flint glass vials stoppered with butyl stoppers and sealed with aluminum seals.
- **Appearance:** clear to opalescent, colorless to pale yellow liquid. May contain particles

### **9.3 STORAGE CONDITIONS:**

Investigational product must be stored at 2-8 degrees C (36-46 degrees F) and protected from light and freezing.

If stored in a glass front refrigerator, vials should be stored in the carton. Recommended safety measures for preparation and handling of nivolumab include laboratory coats and gloves. For additional details on prepared drug storage and use time of nivolumab under room temperature/light and refrigeration, please refer to the BMS-936558 (nivolumab) Investigator Brochure section for “Recommended Storage and Use Conditions”

### **9.4 LABELING:**

Nivolumab may be labeled as BMS-936558-01 Solution for Injection.

### **9.5 HANDLING AND DISPENSING**

The investigator should ensure that the study drug is stored in accordance with the environmental conditions (temperature, light, and humidity) as per product information and the Investigator Brochure and per local regulations. It is the responsibility of the investigator to ensure that investigational product is only dispensed to study subjects. The investigational product must be dispensed only from official study sites by authorized personnel according to local regulations. If concerns regarding the quality or appearance of the study drug arise, the study drug should not be dispensed and contact BMS immediately.

Please refer to the current version of the Investigator Brochure and/or shipment reference sheets for additional information on storage, handling, dispensing, and infusion information for nivolumab.

### **9.6 DESTRUCTION**

Sponsor/Investigator drug destruction is allowed provided the following minimal standards are met:

- On-site disposal practices must not expose humans to risks from the drug.
- On-site disposal practices and procedures are in agreement with applicable laws and regulations, including any special requirements for controlled or hazardous substances.
- Written procedures for on-site disposal are available and followed. The procedures must be filed with the Sponsor SOPs and a copy provided to BMS upon request.
- Records are maintained that allow for traceability of each container, including the date disposed of, quantity disposed, and identification of the person disposing the containers. The method of disposal, ie, incinerator, licensed sanitary landfill, or licensed waste disposal vendor must be documented.
- Accountability and disposal records are complete, up-to-date, and available for BMS to review throughout the clinical trial period as per the study agreement.

If conditions for destruction cannot be met, please contact BMS.

It is the Sponsor Investigator's responsibility to arrange for disposal of all empty containers, provided that procedures for proper disposal have been established according to applicable federal, state, local, and institutional guidelines and procedures, and provided that appropriate records of disposal are kept.

## **10 DEFINITION OF ENDPOINTS**

### **10.1 PRIMARY EFFICACY ENDPOINT**

The primary efficacy endpoint is objective response rate: pathologic complete response + pathologic partial response. Objective response rate: the sum of patients with either a pCR defined as no invasive and no in situ residuals present in the surgical specimen or partial pathologic response defined at least a 30% reduction in the size of the lesion in the surgical specimen. The reduction in size will be determined by comparing the pretreatment clinical measurements (the sum of the greatest axial measurement obtained radiographically, or using calipers if necessary, at the time of initial evaluation) with the final pathologic measurements. Partial response has been chosen as an efficacy endpoint because of the two stage design and small sample size of the proposed trial (*i.e.* a objective response must be observed in at least 1 patient in first nine to proceed with the second stage). The proposed study is based on the current available head and neck squamous cell carcinoma data and is not powered to assess an objective response rate defined as pathologic complete response + major pathologic response.

### **10.2 SECONDARY EFFICACY ENDPOINTS**

Immune capability will be measured as follows:

1. Levels of Treg cells in pre and post treatment peripheral blood will be evaluated using immunostaining for CD4 and flow cytometric analysis of Foxp3. Differences will be calculated (absolute change and percentage change) between pre and post treatment measures.
2. Levels of activated T-cells in peripheral blood will be assessed using flow cytometry for expression of CD69, IFN  $\gamma$ , T-bet and ICOS in CD4+ cells. Differences will be calculated (absolute change and percentage change) between pre and post treatment measures.

3. Intratumoral immune activity assessed by levels of immune stimulatory cytokines including IL-2, IFN  $\gamma$ , and IL-12 or inhibitory cytokine, IL10 and TGF-beta, in OCSCC tumor lysates will be measured flow cytometrically by cytokine bead array. Differences will be calculated (absolute change and percentage change) between pre and post treatment measures.

Immune reactivity against autologous OCSCC will be measured by T cell responsiveness of their pre and post treatment peripheral blood following a challenge with autologous OCSCC.

1. Expression of IFN  $\gamma$ , IL-2 (Th1 responses) and IL 10 (Th2 responses) in CD4+ cells from peripheral blood of patients following PD-1 inhibition therapy will be compared between pre-treatment peripheral blood samples and post-treatment samples from the same patient.
2. Expression of CD8+ cells expressing granzyme B (cytolytic response) from peripheral blood of patients following PD-1 inhibition therapy will be compared between pre-treatment peripheral blood samples and post-treatment samples from the same patient.

### **10.3 DEFINITION OF SECONDARY OUTCOMES/ENDPOINTS:**

1. Increased immune capability will be defined as decrease in Treg population with subsequent increase in activated T cells population.
2. Immune reactivity will be defined as increased Th1 response and CD8+ cytolytic response following challenge to autologous OCSCC in post treatment peripheral blood relative to pretreatment peripheral blood samples.

### **10.4 SAFETY ENDPOINTS**

Adverse events, assessed using the CTCAE v4, occurring between enrollment and 6 weeks following surgery will be collected.

## **11 STATISTICAL CONSIDERATIONS AND DETERMINATION OF SAMPLE SIZE**

### **11.1 DEFINITION OF EVALUABLE PATIENTS**

#### **11.1.1 EVALUABLE FOR SAFETY**

Any patient who receives one or more doses of nivolumab will be included in the safety population.

#### **11.1.2 EVALUABLE FOR EFFICACY**

Patients who receive at least two doses of nivolumab and undergo surgery will be included in the efficacy population.

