### **6.2 DISCONTINUATION CRITERIA**

Subjects may discontinue study treatment at any time. Subjects may be removed from study for any of the following reasons:

- Radiographic disease progression that is not amendable to resection
- Clinical disease progression that would not benefit from surgery
- Inter-current illness that would, in the judgment of the investigator, affect assessments of clinical status to a significant degree or require discontinuation of study drugs
- Completion of protocol treatment.
- Death
- Subject non-compliance
- Treatment should be permanently discontinued for the following:
  - Any Grade 2 drug-related uveitis or eye pain or blurred vision that does not respond to topical therapy and does not improve to Grade 1 severity within the re-treatment period OR requires systemic treatment
  - Any Grade 3 non-skin, drug-related adverse event lasting > 7 days, with the following exceptions for drug-related laboratory abnormalities, uveitis, pneumonitis, bronchospasm, hypersensitivity reactions, infusion reactions, and endocrinopathies:
    - Grade 3 drug-related uveitis, pneumonitis, bronchospasm, hypersensitivity reaction, or infusion reaction of any duration requires discontinuation
    - Grade 3 drug-related endocrinopathies adequately controlled with only physiologic hormone replacement **do not** require discontinuation

- Grade 3 drug-related laboratory abnormalities **do not** require treatment discontinuation except those noted below
  - Grade 3 drug-related thrombocytopenia > 7 days or associated with bleeding requires discontinuation
  - Any drug-related LFT abnormality that meets the following criteria require discontinuation:
    - AST or ALT > 8 x ULN
    - Total bilirubin > 5 x ULN
    - Concurrent AST or ALT > 3 x ULN and total bilirubin > 2 x ULN
- Any Grade 4 drug-related adverse event or laboratory abnormality, except for the following events which **do not** require discontinuation:
  - Isolated Grade 4 amylase or lipase abnormalities that are not associated with symptoms or clinical manifestations of pancreatitis and decrease to < Grade 4 within 1 week of onset.
  - Isolated Grade 4 electrolyte imbalances/abnormalities that are not associated with clinical sequelae and are corrected with supplementation/appropriate management within 72 hours of their onset
  - Grade 4 lymphopenia or leukopenia

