## 11.2 DATA ANALYSIS PLANS

### 11.2.1 PRIMARY OBJECTIVE

The clinical, radiographic and pathologic response rates will each be estimated with a 95% confidence interval, accounting for the two-stage design [41]. The null hypothesis is a 2% pathological response rate and the alternative is a 25% pathological response rate. If no patients respond in the first nine evaluable patients enrolled, the study will be terminated and we will conclude that there is not sufficient activity to reject the null hypothesis. The trial may pause enrollment after the first nine patients (if needed) to follow the ninth patient for a pathologic response. Note, however, that it is possible that an earlier patient may respond which would negate the need to stop enrollment (e.g. the 2nd patient may respond which would satisfy the criteria of at least one patient response in the first nine patients). If at least one patient has a pathologic response among the first nine evaluable patients enrolled, an additional eight patients will be enrolled. If two or more patients among 17 evaluable patients respond, we will reject the null hypothesis. The reported p-value will be based on two-stage design and any deviations from the intended sample size will be accounted for using the approach by Koyama and Chen [41]. Deviations from the planned sample size would only include the need for replacement patients in the event of a patient withdrawal following a single dose of Nivolumab secondary to toxicity or patient preference. If this were to occur these withdrawn patients would be excluded from the efficacy analysis. Only patients that receive at least 2 doses of Nivolumab will be included in the efficacy analysis. Briefly, Koyama and Chen's approach adjusts the final results of the Simon two-stage design (point estimate, 95% confidence interval, and p-value) by considering the evaluation of the data at the end of the 1st stage of the design. Ignoring the two-stage nature of the design, the estimated response rate (i.e. number of responders divided by the total number of patients at the end of stage 2) tends to underestimate the true response rate. In addition, the p-value and 95% confidence interval based simply on the maximum likelihood estimate using the total number of responses and total sample size will not be valid if the futility stopping evaluation is ignored. The approach for implementing the adjustment can be found here:

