### 11.3 DETERMINATION OF SAMPLE SIZE

This study will enroll up to 19 patients. The Simon two-stage design is based on a total of 17 patients who are evaluable for efficacy. We may enroll up to 19 to allow for up to two patients to be inevaluable.

Without treatment, the rate of response would be expected to be very low (<2%). With treatment, we anticipate a meaningful pathological response rate of 25%. Using a Simon optimal two-stage design with alpha of 4% and power of 91%, we can detect this difference with a sample size of no more than 17 patients. In stage 1, 9 patients will be enrolled. If none respond, the study will be stopped. If one or more responds, we will continue to the 2nd stage and an additional 8 patients will be enrolled. If a total of 2 or more patients respond out of 17 we will reject the null hypothesis and conclude that treatment with Nivolumab results in a meaningful pathological response for patients with HNSCC.

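### The efficacy population in 11.1.2 drops patients with two or more doses who miss surgery through treatment failure, which can only raise the reported pathologic response rate

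*Combined protocol and SAP*

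**What the plan says.** Section 11.1.2 sets two conditions for the efficacy population: "Patients who receive at least two doses of nivolumab and undergo surgery will be included in the efficacy population". Sections 11.2.1 and 11.3 apply the two-stage rule to evaluable patients: nine in stage 1 and 17 in total, with continuation on one or more responses and rejection on two or more. Evaluability for efficacy is defined only in 11.1.2, so both counts rest on it.

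Section 11.2.1 adds "Only patients that receive at least 2 doses of Nivolumab will be included in the efficacy analysis", and says of the sample size: "Deviations from the planned sample size would only include the need for replacement patients in the event of a patient withdrawal following a single dose". Section 11.3 provides two spare places: "We may enroll up to 19 to allow for up to two patients to be inevaluable". It does not say why a patient would be inevaluable.

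Among the reasons for removal, section 6.2 lists "Radiographic disease progression that is not amendable to resection" and "Clinical disease progression that would not benefit from surgery". It also notes that "Subjects may discontinue study treatment at any time".

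Section 10.1 reads response in the resected tissue. A complete response needs a specimen free of residual disease, and a partial response is "at least a 30% reduction in the size of the lesion in the surgical specimen". The primary objective in 2.1 concerns patients whose cancer is surgically amenable. No section says how to count a patient who has had two or more doses but no surgery, beyond the exclusion that follows from 11.1.2.

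**The concern.** The exclusion depends on outcome. Tumour assessment takes place around or after the third dose (5.2, 8.4), so a patient found then to be beyond surgery would normally have had at least two doses. Nivolumab has failed in that patient, and no specimen can show otherwise. Under 11.1.2 the patient is removed from the primary rate and from the stage-1 count of nine, and may be succeeded by someone who does reach surgery.

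At stake is the reported response rate, the main result of a 17-patient trial. There is also a gap in the written rules. Section 11.2.1 recognises only single-dose withdrawals as a cause of deviation from the planned size, while 11.1.2 creates a second class of inevaluable patient. If one occurs, the handling would have to be settled with the outcome in view.

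**Working it through.** **Inputs.** Null rate 2% and alternative 25% (11.2.1, 11.3). Nine patients in stage 1, eight more in stage 2, stop on no response, reject on two or more in total. Stated alpha 4% and power 91% (11.3). Up to 19 enrolled for 17 evaluable (11.3, 11.4). The number of treatment failures without surgery is not given; one and two are assumed, the most that the spare places can absorb.

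**The plan's own figures.** The null is not rejected if stage 1 has no response, or if stage 1 has exactly one and stage 2 has none. So

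P(reject) = 1 − (1−p)^9 − 9p(1−p)^16.

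- p = 0.02: 1 − 0.8337 − 0.1303 = 0.0360.
- p = 0.25: 1 − 0.0751 − 0.0226 = 0.9024 (from unrounded terms).

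The type I error of 3.6% rounds to the stated 4%. Power of 90.2% is slightly below the stated 91%.

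**Effect of the exclusion.** Let f be the share of patients with two or more doses who miss surgery through treatment failure. They are all non-responders, so the rate among those left is p/(1−f), a multiplication by 1/(1−f), which is never below 1. Refilling to 17 evaluable:

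| Failures without surgery | f | Relative inflation | Expected rate if true rate is 25% | Pass stage 1 at true 2% | Reject at true 2% |
|---|---|---|---|---|---|
| 0 | 0 | 0 | 25.0% | 16.6% | 3.6% |
| 1 | 1/18 | 18/17 − 1 = 5.9% | 26.5% | 17.5% | 4.0% |
| 2 | 2/19 | 19/17 − 1 = 11.8% | 27.9% | 18.4% | 4.4% |

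The last two columns use p = 0.02 × 18/17 = 0.0212 and p = 0.02 × 19/17 = 0.0224. For two failures: 1 − 0.8159 − 0.1401 = 0.0440.

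In counts, four responders are reported as 4/17 = 23.5%. With the failures kept in, the figure is 4/18 = 22.2% or 4/19 = 21.1%.

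**Scale.** The exact 95% interval for 4/17, without adjustment for the two stages, is 6.8% to 49.9%.

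**Cost of keeping the failures in 17.** If 25% holds only among resected patients, the rate over all 17 is 0.25(1−f).

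- f = 1/18: p = 0.2361, power 1 − 0.0886 − 0.0286 = 88.3%.
- f = 2/19: p = 0.2237, power 1 − 0.1024 − 0.0350 = 86.3%.

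**The case against.** **The situation may not arise.** Unresectable disease is excluded at entry (4.2), patients who progress are sent to surgery (5.2), and a dose missed for an adverse event also leads to surgery (6). This stands: the documents show that such a patient is possible, not likely. It limits the size, but the rule still has to be fixed before results are known.

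**The target may be resected patients.** Section 3.4 speaks of efficacy in patients undergoing definitive resection, and for that population leaving out unresected patients is not bias. This stands in part. The primary objective in 2.1 describes patients as surgically amenable, which is a property at entry, and against that population the exclusion does bias the rate.

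**Stronger readings that the documents do not support.**

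- A reader might infer that 11.2.1 sets a rival denominator of all patients with two doses. It does not. Its two-dose sentence states a necessary condition, and its decision rule is written for evaluable patients as defined in 11.1.2. The textual conflict is confined to the replacement sentence.
- A reader might take larger inflation from leaving places unfilled; three failures among 17 would turn 4/17 into 4/14, a relative rise of 21.4%. Three exceed the allowance for two inevaluable patients in 11.3 and 11.4, and those sections plan for 17 evaluable.
- A reader might infer that every patient without surgery biases the rate upward. For a patient who declines surgery the true response is unknown, so the direction is too.

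**Conclusion.** The concern holds in a limited form and should be fixed. As written, 11.1.2 removes certain non-responders because treatment failed, and the sample-size sentence in 11.2.1 does not cater for them. The upward direction is certain for patients who miss surgery through progression or other treatment failure, measured against the surgically amenable population in 2.1.

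The size is modest: relative inflation of 5.9% or 11.8% with one or two such patients, and nil with none. Rejection at a true 2% reaches 4.4% at most in these cases, above the stated 4% but below 5%. That calculation takes 2% as the rate in all patients with two or more doses. If 2% is meant for resected patients only, the present rule keeps 3.6%. The reject decision is little affected, and the shift in the rate is small beside an interval of roughly 7% to 50%. It is nonetheless systematic and cheap to avoid.

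**What to change.** In 11.1.2, 11.2.1 and 11.3:

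1. Keep in the primary denominator, as non-responders and without replacement, patients with at least two doses who miss surgery because of progression or other treatment failure. Apply this to both the stage-1 count of nine and the final 17.
2. For patients with at least two doses who miss surgery for other reasons, such as refusal, state the handling in advance, report their number, and give a sensitivity rate counting them as non-responders. Counting them so in the primary analysis is defensible but is a matter of preference.
3. Report the set with two doses and surgery as a sensitivity analysis.
4. Align the replacement sentence in 11.2.1 with 11.1.2 and 11.3, so that the text names every kind of patient who may be inevaluable or replaced.

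The cost is wording in three sections, with no new data. The cap of 19 and the safety boundaries in 11.4 can stay. The reported rate may be slightly lower. If 25% holds only in resected patients, power falls from 90.2% to about 88% or 86% with one or two such failures. Type I error stays at 3.6% if 2% applies to all patients with two doses. If 2% applies only to resected patients, it falls to about 2.9% with two such failures (p = 0.02 × 17/19 = 0.0179).

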#### **11.1.3 EVALUABLE FOR IMMUNE ACTIVATION AND REACTIVITY**

Patients who have received at least two doses of nivolumab and have both a pre-treatment and a post-treatment sample available for measuring immune markers will be included in the analyses for the secondary objectives of the study.

## 11.2 DATA ANALYSIS PLANS

### 11.2.1 PRIMARY OBJECTIVE

The clinical, radiographic and pathologic response rates will each be estimated with a 95% confidence interval, accounting for the two-stage design [41]. The null hypothesis is a 2% pathological response rate and the alternative is a 25% pathological response rate. If no patients respond in the first nine evaluable patients enrolled, the study will be terminated and we will conclude that there is not sufficient activity to reject the null hypothesis. The trial may pause enrollment after the first nine patients (if needed) to follow the ninth patient for a pathologic response. Note, however, that it is possible that an earlier patient may respond which would negate the need to stop enrollment (e.g. the 2nd patient may respond which would satisfy the criteria of at least one patient response in the first nine patients). If at least one patient has a pathologic response among the first nine evaluable patients enrolled, an additional eight patients will be enrolled. If two or more patients among 17 evaluable patients respond, we will reject the null hypothesis. The reported p-value will be based on two-stage design and any deviations from the intended sample size will be accounted for using the approach by Koyama and Chen [41]. Deviations from the planned sample size would only include the need for replacement patients in the event of a patient withdrawal following a single dose of Nivolumab secondary to toxicity or patient preference. If this were to occur these withdrawn patients would be excluded from the efficacy analysis. Only patients that receive at least 2 doses of Nivolumab will be included in the efficacy analysis. Briefly, Koyama and Chen's approach adjusts the final results of the Simon two-stage design (point estimate, 95% confidence interval, and p-value) by considering the evaluation of the data at the end of the 1st stage of the design. Ignoring the two-stage nature of the design, the estimated response rate (i.e. number of responders divided by the total number of patients at the end of stage 2) tends to underestimate the true response rate. In addition, the p-value and 95% confidence interval based simply on the maximum likelihood estimate using the total number of responses and total sample size will not be valid if the futility stopping evaluation is ignored. The approach for implementing the adjustment can be found here:

<http://biostat.mc.vanderbilt.edu/wiki/Main/TwoStageInference>

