## **11.5 INTERIM ANALYSIS**

There are no interim analyses planned for this study. However, given that the study design is a Simon two-stage design, the number of responses in the first nine patients will be evaluated and the study will be terminated after the ninth patient if none of these nine patients have achieved a clinical response.

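### Section 11.2.1 applies the two-stage adjustment to all three response rates, although it fits only the one endpoint that drives the stage-1 stop; for the other rates it breaks down at 0 of 17

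*Combined protocol and SAP*

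**What the plan says.** Section 11.2.1 opens with the sentence on intervals: "The clinical, radiographic and pathologic response rates will each be estimated with a 95% confidence interval, accounting for the two-stage design". The method it cites for this is that of Koyama and Chen, which corrects the point estimate, the interval and the p-value for the look at the end of stage 1.

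The rest of Section 11.2.1 concerns pathologic response alone. The hypotheses are set there: "The null hypothesis is a 2% pathological response rate and the alternative is a 25% pathological response rate". So is the continuation rule: "If at least one patient has a pathologic response among the first nine evaluable patients enrolled, an additional eight patients will be enrolled". Section 10.1 agrees, saying that "a objective response must be observed in at least 1 patient in first nine to proceed with the second stage", where objective response is defined as pathologic complete plus pathologic partial response. Section 11.3 sizes the design on the pathologic rate.

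Section 11.5 names a different endpoint: "the study will be terminated after the ninth patient if none of these nine patients have achieved a clinical response". No section makes radiographic response the basis for stopping. No section says what to report for a rate whose own responders do not match the stage-1 decision.

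**The concern.** The adjustment is built on a particular set of possible outcomes: no responder among the first nine means the trial ended at nine, and 17 patients means at least one responder among the first nine. That holds by construction for the endpoint that governs the stop and for no other.

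A pathologic responder need not be a radiographic responder. Restaging scans fall on Days 29-36 (Section 8.4), while the pathologic measurement comes from surgery on Days 36-42 or 50-56 (Section 5.2). The trial can therefore reach 17 patients with no radiographic responder, or stop at nine with one. The plan prescribes a method that does not allow for either outcome, so the analyst would have to choose a substitute after seeing the data. What is at stake is the reporting of two response rates, not the primary test.

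**Working it through.** **Inputs.** n1 = 9, continue if at least 1 responds, n2 = 8, reject at 2 or more of 17, p0 = 2%, p1 = 25% (Sections 11.2.1 and 11.3). The documents give no radiographic or clinical response rate and no correlation with pathologic response. Below, r is an assumed rate for such a second endpoint, and the pathologic rate is taken as 25%.

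**1. The plan's own figures.** P(reject) = 1 − (1−p)^9 − 9p(1−p)^16.
- p = 0.02: 0.1663 − 0.1303 = 0.036, which rounds to the stated alpha of 4%.
- p = 0.25: 0.9249 − 0.0226 = 0.902, against a stated power of 91%. The small difference does not bear on this point.

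**2. The adjusted interval.** At the planned 9 + 8 patients, it was formed by setting P(X1 ≥ 1 and X ≥ x) equal to 0.025 and 0.975, where X1 is the count in the first nine and X the total. The median estimate sets the same probability to 0.5. Only the total x enters, so a rate with no responder among the first nine but one or more later still gets an interval.

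For x = 1 the probability is 1 − (1−p)^9, which gives:
- lower limit 1 − 0.975^(1/9) = 0.28%
- median 1 − 0.5^(1/9) = 7.4%
- upper limit 1 − 0.025^(1/9) = 33.6%

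For x = 0 the condition X ≥ 0 adds nothing, the expression is the same, and so is the answer. An observed 0% is then reported as 7.4% with an interval that excludes 0. The exact (Clopper-Pearson) upper limit is 1 − 0.025^(1/17) = 19.5%.

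| Responders of 17 | Adjusted 95% interval | Exact 95% interval |
|---|---|---|
| 0 | 0.28-33.6% (not meaningful) | 0-19.5% |
| 1 | 0.28-33.6% | 0.15-28.7% |
| 2 | 1.6-34.7% | 1.5-36.4% |
| 3 | 3.9-38.5% | 3.8-43.4% |
| 4 | 6.9-44.0% | 6.8-49.9% |

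With a more conservative upper limit, the adjusted upper bounds for 1 to 4 responders become 34.7%, 38.5%, 44.0% and 50.1%, close to the exact ones from three responders up.

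**3. Chance of 0 of 17, given that the trial continues.**
- Nested (every second-endpoint responder is also a pathologic responder): (1−r)^8 × [(1−r)^9 − 0.75^9] / (1 − 0.75^9).
- Independent: (1−r)^17.

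| r | Nested | Independent |
|---|---|---|
| 5% | 40% | 42% |
| 10% | 15% | 17% |
| 15% | 5% | 6% |
| 20% | 1% | 2% |
| 25% | 0% | 0.8% |

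**4. Stopping at nine with a second-endpoint responder.** Under independence this has probability 0.75^9 × [1 − (1−r)^9]: 2.8%, 4.6%, 5.8% and 6.9% of trials at r = 5%, 10%, 15% and 25%. It is zero under nesting. The exact interval on nine patients is always available (0 of 9: 0-33.6%).

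**5. Coverage.** Exact joint binomial calculations used pathologic rates of 10% and 25%, r from 5% to 25%, and several correlations. Among trials that continued with at least one second-endpoint responder, the adjusted interval covered the true rate 96.4% to 99.1% of the time. Overall coverage of the exact interval in the same cases was 97.8% to 99.3%.

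**The case against.** The strongest reply is that little goes wrong in practice. Much of it stands.

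- **Computability.** A reader might infer that the interval cannot be computed once the first nine contain no radiographic responder. Given continuation, that event has probability 60%, 34%, 17% and 6% (nested) or 63%, 39%, 23% and 13% (independent) at r = 5%, 10%, 15% and 20%. At the planned sample size, however, the calculation uses the total count, so only 0 of 17 fails.
- **Error rates.** A reader might infer that the intervals are wrong in general. No coverage below 95% was found. Even the mechanical interval at 0 of 17 contains every assumed rate from 5% to 25%. The fault there is the reported estimate and the exclusion of the observed value.
- **Frequency.** A reader might infer that failure is common. That depends on rates the documents do not give. The nearest figure is the hypothesized 25-30% overall response in Section 3.4, and at 25% the failure is rare.
- **Clinical response.** It cannot be said flatly that clinical response plays no part in the stop, because Section 11.5 says it does. This does not rescue the plan: whichever endpoint governs, the other two do not.
- **The replacement.** A fixed-sample exact interval also ignores the stop, which matters somewhat for a correlated endpoint. It is nevertheless always defined and kept its coverage here.
- **Importance.** The hypotheses and the rejection rule rest on pathologic response, and the other two rates are not among the secondary endpoints in Sections 10.2 and 10.3. This limits the weight of the point but does not remove it.

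**Conclusion.** The point holds in a limited form. Section 11.2.1 prescribes a correction for at least two rates that the stage-1 rule does not govern. This is certain for radiographic response; for clinical response it depends on how Section 11.5 is reconciled with Sections 10.1 and 11.2.1.

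The consequence is a material difference at low counts and a misleading result at 0 of 17. How likely that result is rests on an assumed 25% pathologic rate and an unstated second-endpoint rate: a serious possibility if the latter is 5-10%, negligible at 25%. The interval's form was taken as in step 2 of the working, at exactly 9 + 8 patients. The documents do not support a claim that the intervals are generally invalid or usually undefined. The primary analysis is not affected.

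**What to change.** In Section 11.2.1, restrict the Koyama-Chen estimate, interval and p-value to the endpoint that governs stage 1, which is pathologic response as Sections 10.1, 11.2.1 and 11.3 have it. Report the other two rates as observed proportions with exact Clopper-Pearson 95% intervals on the patients observed, labeled descriptive, with a note that the stage-1 decision was made on another endpoint. Reconcile the stopping endpoint in Section 11.5 with those sections.

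The cost is a sentence in Section 11.2.1 and a wording correction in Section 11.5, with no change to patients, data or design. The small downside is that the descriptive intervals are not exact for an endpoint correlated with the stop.
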